## 1.4 RANDOMIZATION AND MASKING

NA

## 1.5 CHANGE OF STATISTICAL ANALYSIS PLAN IN PROTOCOL

### 1.5.1 Change in Protocol Amendment

NA

### 1.5.2 Changes in Statistical Analysis Plan

See version history.

## **2 Endpoints**

Assessment schedule for each endpoint collected is described in Appendix 1.

### **2.1 PRIMARY EFFICACY ENDPOINT**

ORR as estimated by binomial distribution.

### **2.2 SECONDARY ENDPOINT**

TTR、DOR、PFS、OS and 6 months PFS rate and OS rate.

### **2.3 SAFETY ENDPOINT**

Incidence rates of all adverse events (AE), treatment emergent adverse event (TEAE), adverse event of special interest(AESI) and serious adverse event (SAE), relationship to study treatment and severity. Changes in vital signs, physical exam and clinical laboratory evaluation before and after study treatment.

### **2.4 IMMUNOGENICITY ENDPOINT**

Anti drug antibody (ADA) and neutralizing antibody (NAb) will be tested.

### **2.5 PHARMACODYNAMIC ENDPOINT**

NA

### **2.6 QUALITY OF LIFE ENDPOINT**

Qualifty of life will be evaluated by EQ 5D-5L and EORTC QLQ-C30 changen over time.

### **2.7 BIOMARKER ANALYSIS:**

Biomarker samples will be collected to analyze PD-L1 expression in tumor tissues and RNA sequence and TILs.

Blood samples will be analyzed for peripheral blood EBV-DNA changes over time, immune cell changes, immune-related cytokine changes and correlation with efficacy.

## **3 Analysis Population**

### **3.1 ANALYSIS SET**

Analysis sets include Safety set (SS), full analysis set (FAS), per protocol set (PPS):

1) SS: Subjects receiving at least one dose of study treatment

- 2) FAS: Subjects receiving at least one dose of study treatment and with measurable disease at baseline. Subjects may be excluded if not satisfying ENKTL criteria by central pathological review.
- 3) PPS: Subset of FAS and without major protocol deviation nor use of prohibited medication nor poor compliance.

### 3.2 MAJOR PROTOCOL DEVIATION

Major protocol deviation is defined as deviation will have important impact on efficacy. In this study, deviations listed below are considered as major and subjects with major deviation will not be included in PPS:

- Do not meet major inclusion/exclusion criteria;
- Use of prohibited medication;
- Poor compliance (<80% or >120%, less than 2 cycles of treatment);
- Actual received treatment is different from being assigned.

Major protocol deviations will be reviewed at Blind Data Review Meeting (BDRM) and listed before database lock.

Major protocol deviation will be listed with detailed descriptions.

## 4 Data Handling Convention

### 4.1 GENERAL RULES

- **Observation Period Definition**

Observation period is defined as:

**Screening period:** from inform consent to first dose of study treatment.

**On-treatment period:** from first dose to last dose.

**Treatment residual period:** last dose +1 to last dose + 90 days.

Treatment emergent period include both on-treatment period and treatment residual period.

**Post-treatment period:** from last dose+91 days to end of study.

### 4.2 SPECIAL HANDLING OF EFFICACY DATA

NA

### 4.3 MISSING VALUE AND EXTREM VALUES

Missing of date variables: if the date is partial or incomplete, the imputation will be done based on the following rules following appropriate logic:

- if year, month and date are all missing, then do not impute;

## STATISTICAL ANALYSIS PLAN

Innovent Biologics (Suzhou) Ltd  
Protocol number: CIBI308D201

Version: 2.0  
Version Date: 2020-02-28

---

- if month and date are missing, it will be assumed as July 1st with no conflict with other date variables;
- if dates are missing, it will be assumed as 15th with no conflict with other date variables;
- Original date collected from CRF will be shown in the listings.
- Missing data handling of other variables

Efficacy variables: All missing in the primary efficacy endpoints due to early withdrawal or lost follow up will be treated as "unable to evaluate ". In the calculation of time to event variables (e.g. PFS, DOR), subjects who have tumor evaluation missing after treatment will be reviewed to determine the time of censoring during data review meeting prior to database lock.

There will be no missing value imputation for baseline and safety data.

The extreme value of laboratory data identified as being caused by improper handling of specimens and blood samples will be replaced by unplanned visit data in the visit window (if available) as defined by the protocol. If these values cannot be replaced, they will be set as missing and be excluded from the analyses.

- Definition of baseline

The last non-missing data before first study drug administration will be defined as the baseline.

- Data derivation rules

Age (year) = (Informed Consent Date of Signature – Birth Date +1)/365.25, round to 1 decimal digits;

Course of first diagnosis (Day) = Informed Consent Date of Signature – Birth Date +1;

For efficacy related data derivation, see the sections which define efficacy endpoints.

- **Missing Relationship of AE to Study Treatment**

If relationship is missing, no imputation is made but will be considered as related.

- **Missing CTCAE grade**

Missing grade will not be imputed but will be counted in summary as grade  $\geq 3$  and will be listed separately.

- **Handling of Outliners**

NA

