### 5.5.2 Secondary Analysis

DCR

$$DCR = \frac{CR + PR + SD}{\text{Total Number of Subjects}} * 100\%, \text{ and 95\% CI will be calculated using binomial distribution.}$$

PFS

PFS: the time from the date of the first dose to the date of first disease progression (imaging), if subjects died due to any reason prior to disease progression, PFS is defined as the time from the date of the first dose to the date of death. Subjects who did not die or had disease progressed will be censored on the date of the last imaging assessment date. Subjects with no post-baseline imaging assessment will be censored on the date of the first dose of study medication. Subjects treated with other anti-cancer therapy before PD will be censored at last non-missing tumor assessment date before starting of the new anti-cancer therapy.

Kaplan-Meier method will be used for the analysis of PFS to evaluate the median PFS (mPFS), PFS rate at 6 month and at 1 year, and its 95% CI and the survival curves will be provided accordingly.

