#### DOR

For subjects with complete response or partial response, the duration of response is defined as the time from the date of first response to the date of disease progression or death whichever is earlier, and subjects with no disease progression or death will be censored on the date of the last imaging assessment.

Kaplan-Meier method will be used for the analysis of DOR to evaluate the median DOR and its 95% CI and the survival curves will be provided accordingly.

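### SAP 4.3 leaves PFS and DoR censoring times for subjects with missing tumor evaluations to a pre-lock meeting with no criterion, although SAP 5.5.2 already states fixed dates

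*SAP*

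**What the plan says.** SAP 4.3 (missing and extreme values) deals with missing efficacy data in two parts. Missing primary-endpoint data after early withdrawal or loss to follow-up are classed as not evaluable. For time-to-event variables, with PFS and DoR named as examples, "subjects who have tumor evaluation missing after treatment" "will be reviewed to determine the time of censoring during data review meeting prior to database lock". No criterion, default date or decision-maker follows. Further down, under data derivation, the same section adds: "For efficacy related data derivation, see the sections which define efficacy endpoints".

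SAP 5.5.2 states the dates outright.

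- PFS, no progression or death: "Subjects who did not die or had disease progressed will be censored on the date of the last imaging assessment date".
- PFS, no scan after baseline: "Subjects with no post-baseline imaging assessment will be censored on the date of the first dose of study medication".
- PFS, other anti-cancer therapy before progression: the subject "will be censored at last non-missing tumor assessment date before starting of the new anti-cancer therapy".
- DoR: "subjects with no disease progression or death will be censored on the date of the last imaging assessment".

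SAP 4.2, on special handling of efficacy data, is marked not applicable. Protocol 8.6.1 states that the study is single-arm and open-label, without randomization or blinding.

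**The concern.** A date that 5.5.2 fixes does not need a meeting to determine it. As written, two sections of the SAP govern the same subjects differently, and the one that addresses missing evaluations contains no rule.

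In a blinded randomized trial, a data review before lock is protected because the reviewers do not know the treatment. Here there is one arm and no blinding, so progression, death and later therapy are visible. A censoring time settled at that point can be settled with the subject's outcome in view, and two statisticians working from the SAP could not be sure of obtaining the same PFS or DoR curve. PFS, 6-month PFS and DoR are named secondary objectives, and DoR helps a reader judge what a single-arm response rate is worth.

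**Working it through.** **Plan's own figure.** The plan gives no power or precision figure for PFS or DoR. Its only design figure is 43 subjects for ORR (Protocol 8.5, SAP 1.3): 30% against 50%, two-sided 0.05, 80% power. By the normal approximation, n = ((1.960·√(0.3·0.7) + 0.842·√(0.5·0.5))/0.2)² = 43.49, which agrees with 43 to within one subject. Censoring dates do not enter this calculation.

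**What the two sections give under each reading of missing evaluations after treatment.** The phrase in 4.3 is not defined.

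| Reading | Date under 5.5.2, PFS | Date under 5.5.2, DoR | Date under 4.3 |
|---|---|---|---|
| No scan after baseline | First dose | Not applicable: a responder has had a scan | Set by meeting |
| Scans missed or stopped, no PD or death | Last imaging | Last imaging | Set by meeting |
| New therapy before PD | Last assessment before that therapy | No specific rule | Set by meeting if evaluations are missing |
| PD or death recorded after missed scans | Event, by the definition of PFS | Event, by the definition of DoR | Not stated |

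So 5.5.2 gives a PFS date in every censored row. Its DoR text lacks the new-therapy rule. Neither section says expressly how progression or death after missed scans is dated, although the definitions in 5.5.2 make it an event. There is also a conflict between documents in the first row: Protocol 8.4.3 censors PFS at enrollment, the SAP at first dose.

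**Scale, on assumed data.** The scan weeks 6, 15 and 24 are from Protocol 6.3. The 28 subjects are the number enrolled when enrollment was paused (Protocol, Summary of Amendment); the planned range is 20 to 60. Everything else is assumed: 4 subjects have missed scans; of the other 24, 6 progress at week 6, 4 at week 15 and 2 at week 24, and 12 are censored at week 36. Subjects censored at an event time count as at risk at that time. The Kaplan-Meier estimate at 26 weeks is then:

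- the 4 censored at day 1: (18/24)(14/18)(12/14) = 50.0%
- at week 6: (22/28)(14/18)(12/14) = 52.4%
- at week 15: (22/28)(18/22)(12/14) = 55.1%
- at week 24: (22/28)(18/22)(16/18) = 57.1%

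The range is 7.1 points. If the last scan of all four was at week 6, 5.5.2 gives 52.4%, and other dates move the estimate by −2.4 to +4.8 points.

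In general, with n subjects, k of them with missed scans and D events among the other n − k, the span from earliest to latest censoring is D/(n − k) − D/n = Dk/[n(n − k)]. With n = 28:

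- k = 2, D = 13: 26/728 = 3.6 points
- k = 3, D = 12: 36/700 = 5.1 points
- k = 4, D = 12: 48/672 = 7.1 points
- k = 6, D = 11: 66/616 = 10.7 points

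**The case against.** The strongest defence is that nothing in the SAP ranks 4.3 above 5.5.2, and that 4.3 itself sends efficacy derivations to the endpoint sections. On that reading the meeting only confirms which 5.5.2 rule applies. The provision also covers only subjects with missing evaluations; on its narrowest reading (no scan after baseline) PFS already has a date and DoR is untouched. Decisions are taken before lock, and the endpoints carry no hypothesis test.

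Much of this stands. A reader might infer that 4.3 overrides 5.5.2, but the text does not say so; the relation is simply unstated. The defence does not make the sentence harmless, however. The pointer sits under data derivation, apart from the missing-data text. If 5.5.2 governs, the meeting sentence has no function; if it does not, the date is discretionary. Either way the same edit is needed. Timing before lock is only partial protection when nothing is blinded.

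Three other strong readings are not supported:

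- A reader might infer that the meeting is labelled blind and that everyone present knows each outcome. SAP 3.2 uses the word blind for the meeting that reviews protocol deviations; 4.3 does not use it. That the two are one meeting is an inference, and no section says who attends or what they see. The documents support only that outcomes can be known.
- A reader might take 5.5.2 to settle every case. It does not: DoR has no new-therapy rule.
- A reader might size the effect as 1/28 = 3.6 points per subject. That is the change in a crude proportion when a subject moves between progressed and progression-free. The 4.3 sentence concerns the time of censoring; in the illustration that is worth at most 7.1/4 = 1.8 points per subject.

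**Conclusion.** The point holds in a limited form. SAP 4.3 provides for a decision on censoring time without a criterion, beside fixed dates in 5.5.2, with no order of precedence and no blinding. It should be corrected.

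The effect is confined to PFS, 6-month PFS and DoR. The ORR test and the sample size do not depend on it, because 4.3 handles missing primary-endpoint data separately.

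On the assumed data, 26-week PFS moves within 50.0% to 57.1% with 4 affected subjects, and the span is about 4 to 11 points for 2 to 6. These figures rest on the assumed event pattern, on 28 subjects, and on all affected subjects being moved together from the earliest to the latest date. The documents do not report how many subjects missed scans, so this is a range of sensitivity and not a predicted bias. Nothing in the documents shows the direction of any bias, or that dates were in fact chosen with outcomes in view.

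**What to change.** Delete the meeting sentence in SAP 4.3 and replace it with wording to this effect: event and censoring dates for all subjects, including those with missed tumor evaluations, follow 5.5.2; documented progression or death counts as an event as 5.5.2 defines it; the data review meeting may confirm data but does not set dates. The middle clause matters, because a bare instruction to censor subjects with missing evaluations under 5.5.2 could be read as censoring someone who missed a scan and later progressed or died.

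In the same edit:

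- apply the PFS rule on new anti-cancer therapy to DoR;
- reconcile the PFS date for subjects with no post-baseline imaging (enrollment in Protocol 8.4.3, first dose in SAP 5.5.2);
- put any alternative dating, for example of events found after missed scans, in a sensitivity analysis labelled as such.

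The cost is a few sentences in the SAP, with a matching line in the protocol if its date is the one changed. No new data are needed.

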#### **4.4 TIME WINDOWS**

First dose date of the study treatment is defined as Day 1. Visit day definition: measurement date – first dose date +1; if measurement date is before first dose date, then visit day is defined as measurement date-first dose date.

All data will be analyzed according to flowchart and nominal visit name on eCR. No visit window will be applied.

Unscheduled visit will be used for baseline calculation. There will be no analysis over time for clinical laboratory evaluation, vital sign, ECG. Therefore no time window will be applied. Summary by all post-baseline results and worst post-baseline results will be analyzed.

#### **4.5 STUDY CENTER EFFECT**

NA

### **5 Statistical Methods**

#### **5.1 GENERAL RULES**

All the statistical analyses will be performed with SAS 9.2 (or higher).

Unless otherwise stated, all TFLs will follow the rules below:

- Baseline value: last available data before first dose.
- Significant level and multiplicity adjustment: 5% two-sided level, no adjustment will be made.
- Summary statistics for continuous variables: N, mean, standard deviation, median, Q1, Q3, min and max.
- Categorical variables: number of subjects and percentage.
- Denominator in percentage calculation: unless otherwise specified, subjects with missing values will not be included. Number of subjects with missing value will be provided.

#### **5.2 SUBJECT DISPOSITION**

##### **Subject Disposition**

Number and percentage of subjects enrolled, treated, treatment continued after PD, early discontinuation of treatment will be summarized. The above information will also be summarized by study centers.

Listing will be provided for subject discontinued early.

In percentage calculation described above (except for screen failure and enrollment rate), denominators will be number of subjects receiving study treatment. In by center summary, number of subjects in each major category (screened, treated, discontinued, end of study, treated beyond PD, analysis population) will be provided.

### **Protocol Deviations**

Summary will be provided for number and percentage of subjects with major protocol deviation. Listing will be provided for subjects with major protocol deviation and inclusion/exclusion criteria deviation.

## **5.3 DEMOGRAPHICS AND DISEASE CHARACTERISTICS**

### **5.3.1 Demographics and Disease Characteristics**

Demographics and disease Characteristics will be summarized in SS, FAS and PPS for the following variables:

- Age, Sex, Ethnicity
- Smoking history: smoking status, daily smoking quantity, duration of smoking, time since ceasing smoking
- Allergy history: percentage of subjects with allergy history and allergy type
- Baseline height, weight, BMI, BSA
- Baseline vital signs SBP, DBP, pulse, temperature, respiratory
- Baseline ECOGS PS
- Baseline physical exam: N and percentage for each exam item
- Baseline virology exam and HBV, HBV DNA, HCV RNA
- Baseline anti-auto antibody

### **5.3.2 Medical History**

- **Disease Diagnosis**
- Cancer related disease history: including time since first diagnose, disease stage, pathological stage, disease range, histological subtype.
- Anti-cancer therapy history: History of anti-cancer systemic therapy (number of chemotherapy regimens, treatment cycles, treatment type, best response), history of anti-cancer radiotherapy (site of radiotherapy, total dosage, treatment type and best response) and other therapies (treatment, best response)

- Baseline target lesion number and non-target lesion numbers, locations, sum of diameters

Following variables will be summarized by descriptive statistics: Disease duration=date of inform consent-earlier time between initial diagnosis and start of prior therapy+1

- **Other Medical History**

The disease will be coded according to the MedDRA term, and the proportion of subjects with each disease will be summarized according to the preferred term (PT), including: prior disease recovered: A disease that has been cured in a medical history, ongoing disease: a disease no cured, a disease undergoing treatment: a disease undergoing medical treatment.

- **Prior and Concomitant Medication (other than anti-cancer)**

Prior and concomitant medications will be coded using The World Health Organization Drug Dictionary (WHODD) and will be summarized by Anatomical Therapeutic Chemical (ATC) class 1, 2, 4 and preferred name (PN). One subject is only counted once for each corresponding category/PN.

Prior medications: medications which started and stopped prior to the first dose of study medication, stop date – date of first dose of study medication < 0;

Concomitant medications: start date – date of first dose of study medication < 0, and (start date-date of last dose+90)>=0 and stop date – date of first dose of study medication >= 0;

New concomitant medications: medications newly added or changed during the study period, start date – end date of first dose of study medication >= 0 and (start date-date of last dose+90)>=0.

Post study medications: medications started after last dose of study treatment+90 days.

If the start date is missing, the medication will be considered as “concomitant medication”, unless the stop date is non-missing and the stop date is prior to date of first dose of study medication

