### **5.6.1 Adverse Events**

All adverse events will be coded using MedDRA dictionary for lower level term (LLT), preferred term (PT), high level term (HLT), high level group term (HLGT) and system organ class (SOC). AE

reporting period will be further defined based on onset date/becoming serious/becoming more severe as:

- Pre-treatment AE: AE occurs/becomes serious/becomes more severe before first dose of treatment and after inform consent.
- Treatment-emergent AE: AE occurs/becomes serious/becomes more severe on or after date of first dose of treatment up to last dose of study treatment+90 days
- Post treatment AE: AE occurs/becomes serious/becomes more severe on or after date of last dose of study treatment+91 days

If onset date of AE is missing or partial missing, determination of AE reporting period will be based on rules in Section 4.3.

- **Overview of adverse event**

Listing will be provided for pre-treatment and post-treatment AE.

Number and percentage of subjects who experience AE and event frequency will be summarized for:

- Treatment emergent period
  - TEAE
  - Treatment related AE (TRAE)
  - Serious AE (TESAE)
  - AE leading to death
  - TRSAE
  - TRAE leading to death
  - TEAE leading to treatment discontinuation
  - TRAE leading to treatment discontinuation
  - Important AE (Chinese regulator specific requirement only)
  - Immune-related AE (irAE)

Unless otherwise stated, SOC/PT summary will be sorted according to descending order of frequency.

- **TEAE analysis**

Number and percentage of subjects with AE will be summarized by:

- SOC and PT and by highest CTCAE grade for TEAE

- SOC and PT and by highest CTCAE grade for TRAE
- SOC and PT and by highest CTCAE grade for TEAE leading to treatment discontinuation
- SOC and PT and by highest CTCAE grade for TRAE leading to treatment discontinuation
- SOC and PT and by highest CTCAE grade for important AE (Chinese regulator specific requirement only)
- PT for TESAE
- PT for infusion-related reactions(IRR)
- **Immune-related treatment emergent AE and AE of special interest**

Immune-related treatment emergent AE:

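### SAP 5.3.2 applies last dose + 90 days as a lower instead of an upper limit on medication start, and the SAP 4.3 rule for course of first diagnosis computes age in days

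*SAP*

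**What the plan says.** SAP 5.3.2 sorts non-anti-cancer medications into four classes.

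- *Prior*: started and stopped before first dose.
- *Concomitant*: started before first dose, stopped on or after it, and subject to a further date condition, "date of first dose of study medication < 0, and (start date-date of last dose+90)>=0".
- *New concomitant*: added or changed during the study, with the condition "start date – end date of first dose of study medication >= 0 and (start date-date of last dose+90)>=0".
- *Post study*: "Post study medications: medications started after last dose of study treatment+90 days".

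A missing start date has its own default: "If the start date is missing, the medication will be considered as" concomitant, unless the stop date is known and precedes first dose.

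The same 90-day limit appears twice more. SAP 4.1 sets the treatment residual period as "last dose +1 to last dose + 90 days". SAP 5.6.1 counts an adverse event as treatment-emergent if it occurs "on or after date of first dose of treatment up to last dose of study treatment+90 days".

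On diagnosis, the derivation rules in SAP 4.3 give "Age (year) = (Informed Consent Date of Signature – Birth Date +1)/365.25" and, on the next line, "Course of first diagnosis (Day) = Informed Consent Date of Signature – Birth Date +1". SAP 5.3.2 lists time since first diagnosis as a baseline variable. It also defines disease duration as consent date minus the earlier of initial diagnosis and start of prior therapy, plus 1.

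**The concern.** In SAP 4.1, in SAP 5.6.1 and in the post-study rule, last dose + 90 days closes a window. In the two concomitant-medication formulas the inequality points the other way and sets an earliest start date. Three things follow if the formulas are coded as written.

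- A drug begun before first dose and continued past it can have no class. It is not prior, because it did not stop before first dose, and it can fail the concomitant condition. Protocol 5.5.2 permits long-term medication for conditions such as hypertension and diabetes, so this is an ordinary case.
- A drug begun early in a long course of treatment drops out of the new-concomitant class.
- The new-concomitant class has no upper limit, so it overlaps the post-study class.

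The missing-date default makes the result odder still: an undated drug is tabulated while a fully dated chronic one may not be.

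The SAP 4.3 line has a different fault. It contains no diagnosis date, and the SAP does not say whether this line or the disease-duration formula produces time since first diagnosis.

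At stake are the medication summaries by ATC class and preferred name, and one baseline row. Protocol 8.4.9 plans description of both past/concomitant medications and tumor diagnosis information.

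**Working it through.** The documents give no figure for these rules, so there is none to reproduce. The check solves the inequalities and counts calendar days.

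**Inputs.** First dose = day 0 and last dose = day L. Doses are every 21 days (SAP 1.2), so the k-th dose falls on day 21 × (k − 1) if nothing is delayed. Treatment lasts at most 24 months (SAP 1.2); the 35th dose falls on day 714. Age at entry is 18 to 70 (Protocol 4.1).

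**Bracket as written.** start − L + 90 ≥ 0 gives start ≥ L − 90.

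- *Concomitant* also needs start ≤ −1, so eligible starts run from L − 90 to −1. That is 90 − L days, and none once L ≥ 90. Because L is never below 0, a drug started more than 90 days before first dose and continued past it is unclassified at every treatment length.
- *New concomitant* also needs start ≥ 0. The intended window, day 0 to day L + 90, has L + 91 days. Days 0 to L − 91 are lost, which is L − 90 days when L > 90.
- A start after L + 90 satisfies both the new-concomitant and the post-study rule.

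| Last dose day L | Dose number | Pre-dose start days (of 365) that can be concomitant | In-window start days | Lost from new concomitant |
|---|---|---|---|---|
| 42 | 3rd | 48 | 133 | 0 |
| 84 | 5th | 6 | 175 | 0 |
| 105 | 6th | 0 | 196 | 15 (8%) |
| 168 | 9th | 0 | 259 | 78 (30%) |
| 357 | 18th | 0 | 448 | 267 (60%) |
| 714 | 35th | 0 | 805 | 624 (78%) |

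**Other bracketing.** Reading the term as start − (L + 90) ≥ 0 gives start ≥ L + 90. This is still a lower bound. The concomitant class is then always empty, and new concomitant keeps one in-window day, day L + 90.

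**Reversing the sign alone.** start − L + 90 ≤ 0 gives start ≤ L − 90. New concomitant then keeps 0 of 175 in-window days at L = 84 and 79 of 259 (days 0 to 78) at L = 168. Concomitant at L = 0 keeps only starts from −365 to −90, which is 276 of 365. Grouping and sign must therefore both change.

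**Course of first diagnosis.** The formula is the numerator of the age formula, so it equals age in days: 18 × 365.25 + 1 ≈ 6,576 and 70 × 365.25 + 1 ≈ 25,569. As an illustration, take consent on 1 September 2017, birth on 1 September 1967 and diagnosis on 1 September 2016. The SAP 4.3 rule gives 18,264 days. Consent minus diagnosis plus 1 gives 366 days.

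**The case against.** The best defence is that this is a drafting slip whose intent can be recovered. The wording of the new-concomitant class and the correctly stated post-study rule show what was meant, and an empty concomitant class in longer-treated subjects would probably be caught when programs are checked. No inference depends on it:

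- The section excludes anti-cancer drugs, so it does not feed the PFS censoring rule.
- Per-protocol exclusion for prohibited medication is decided at the data review meeting (SAP 3.2) and is not tied to these classes.

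The percentages count calendar days, not drugs. The documents give no distribution of treatment length, so the 78% case cannot be taken as typical. Many dated drugs are classified correctly: starts on or after first dose that fall from 90 days before to 90 days after last dose, and recent pre-dose starts in subjects with few doses. The overlap with post-study drugs may be rare, since Protocol 6.2.6 asks mainly about survival and anti-tumor therapy, although Table 1 does mark concomitant medication at that visit. The birth-date line may be an orphaned copy of the age line.

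All of this stands as a limit on impact. It does not rescue the text. The same inequality appears twice, no correct version is given anywhere, and changing only the sign or only the bracket still gives wrong classes. No reading turns a birth date into a diagnosis date.

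**Conclusion.** The concern holds. Both medication formulas set a lower bound under either bracketing and contradict the SAP's own use of last dose + 90 days. Coded literally, they leave the concomitant class with no known-date drugs once first-to-last dose reaches 90 days. They also remove 8% to 78% of in-window start days from the new-concomitant class as last dose moves from day 105 to day 714. These sizes assume undelayed dosing and literal programming, and they measure exposure to the error rather than the number of drugs affected. The course-of-first-diagnosis rule is age in days; it harms a table only if it is used for time since first diagnosis, which the SAP leaves open. The consequences are confined to descriptive summaries. No effect on response rate, per-protocol membership or classification of immune-related events has been shown. The text should be corrected, but it is not a threat to the trial's main conclusion.

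**What to change.** In SAP 5.3.2:

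- *Concomitant*: start date before first dose, and stop date on or after first dose or medication ongoing. The 90-day term is not needed here.
- *New concomitant*: start date on or after first dose, and start date − (last dose date + 90) ≤ 0.

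Keep the prior, post-study and missing-start-date rules. Every drug with a known start date then has exactly one class. Starts before first dose divide by whether the drug stopped before first dose, and later starts divide at last dose + 90 days. Writing first dose instead of end of first dose makes no practical difference for an infusion of about 30 to 60 minutes (Protocol 5.2.4).

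In SAP 4.3, either delete the course-of-first-diagnosis line and keep the SAP 5.3.2 disease-duration formula, or replace birth date with date of first diagnosis. In either case, state which rule yields time since first diagnosis, because SAP 5.3.2 counts from the earlier of diagnosis and prior therapy.

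The cost is three lines of SAP text and the corresponding program code. No new data are needed.
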